## **5. STUDY POPULATION**

### **5.1. Participant Recruitment**

The study will enroll approximately 452 adult participants 18-40 years of age, including 252 participants in Part 1 (approximately 180 CMV-seronegative participants and approximately 72 CMV-seropositive participants) and 200 participants in Part 2 (approximately 80 CMV-seronegative participants and approximately 120 CMV-seropositive participants), who will receive mRNA-1647 vaccine or placebo.

The Sponsor may enroll up to 502 participants including 252 participants in Part 1 (approximately 180 CMV-seronegative participants and approximately 72 CMV-seropositive participants) and 250 participants in Part 2 (approximately 100 CMV-seronegative participants and approximately 150 CMV-seropositive participants).

Upon completion of all screening procedures ([Section 8.1](#)), the Investigator will review the inclusion/exclusion criteria for each participant to determine if the participant is eligible. Participants who meet all eligibility criteria will be enrolled in the study.

Their screening information will be recorded on the appropriate page of the electronic case report form (eCRF). Based on prior approval from the Sponsor, the Screening visit may be performed across 2 separate clinic visits.

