4.1. Overall Study Design

This is a Phase 2, randomized, placebo-controlled, observer-blind, dose-finding trial enrolling healthy participants 18-40 years of age.

A schematic of the study design is shown in [Figure 1](#).

Figure 1 Study Design Schematic

Abbreviations: IST= internal safety team; mRNA = messenger ribonucleic acid.

In protocol amendment version 3, Part 2 of the study was added to evaluate the safety and immunogenicity of the selected CCI mRNA-1647 dose level in a larger female population, which is the target population for Phase 3 development.

CMV-seronegative and CMV-seropositive groups will be enrolled at the same time. Randomization will be stratified by CMV serostatus (via an Interactive Response Technology [IRT]) in a sequential manner into the CCI dose levels in Part 1 and the CCI dose level in Part 2. At each dose level, participants will be randomized in 3:1 ratio to either mRNA-1647 vaccine or placebo, administered in a 3-vaccination (0, 2, 6-month) schedule.

Treatment Arms

Part 1 CMV-seronegative Group (males and females aged 18-40 years)

- Approximately 60 participants randomized 3:1 to receive either CCI of mRNA-1647 vaccine or placebo in a 0, 2, 6-month schedule
- Approximately 60 participants randomized 3:1 to receive either CCI of mRNA-1647 vaccine or placebo in a 0, 2, 6-month schedule

- Approximately 60 participants randomized 3:1 to receive either CCI of mRNA-1647 vaccine or placebo in a 0, 2, 6-month schedule

Part 1 CMV-seropositive Group (males and females aged 18-40 years)

- Approximately 24 participants randomized 3:1 to receive either CCI of mRNA-1647 vaccine or placebo in a 0, 2, 6-month schedule
- Approximately 24 participants randomized 3:1 to receive either CCI of mRNA-1647 vaccine or placebo in a 0, 2, 6-month schedule
- Approximately 24 participants randomized 3:1 to receive either CCI of mRNA-1647 vaccine or placebo in a 0, 2, 6-month schedule

Part 2 CMV-seronegative Group (females aged 18-40 years)

- Approximately 80 participants randomized 3:1 to receive either CCI of mRNA-1647 vaccine or placebo in a 0, 2, 6-month schedule

Part 2 CMV-seropositive Group (females aged 18-40 years)

- Approximately 120 participants randomized 3:1 to receive either CCI of mRNA-1647 vaccine or placebo in a 0, 2, 6-month schedule

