5.5. Per-Protocol Sets

The Per-Protocol (PP) Set for Antibody-Mediated Immunogenicity

PP Set for Antibody-Mediated Immunogenicity consist of all FAS participants who

- a) comply with the vaccination schedule,
- b) comply with the timings of immunogenicity blood sampling to have post-vaccination results available for at least one assay component corresponding to the immunogenicity analysis objective (antibody-mediated immunogenicity endpoints), and
- c) have no major protocol deviations that impact immune response during the period corresponding to the immunogenicity analysis objective (antibody-mediated immunogenicity endpoints).

Subjects who were CMV seronegative at Screening and became CMV seropositive at baseline (before or on 1st dose of study vaccination) will be excluded from the PP Set for Antibody-Mediated Immunogenicity.

The PP Set for Antibody-Mediated Immunogenicity will serve as the primary population for the analysis of antibody-mediated immunogenicity data in this study. Participants will be included in the vaccination group to which they are randomized.

PP Set for CMI

PP Set for CMI consist of all FAS for Cell-Mediated participants who

- a) comply with the 3-dose vaccination schedule,
- b) comply with the timings of immunogenicity blood sampling to have post-vaccination results available for at least one assay component corresponding to the immunogenicity analysis objective (CMI endpoints), and
- c) have no major protocol deviations that impact immune response during the period corresponding to the immunogenicity analysis objective (CMI endpoints).

Subjects who were CMV seronegative at Screening and became CMV seropositive at baseline (before or on 1st dose of study vaccination) will be excluded from the PP Set for CMI.

The PP Set for CMI will serve as the primary population for the analysis of CMI data in this study. Participants will be included in the vaccination group to which they are randomized.

6. Statistical Analysis

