- c) study day after the date of the second vaccination but before the third vaccination (if applicable) will be calculated as: date of assessment/event – date of the second vaccination + 1; if study day is on the same day as the second vaccination, date and time will be compared with the second vaccination date and time. If it is prior to the second vaccination, then study day is calculated as [b\)](#); If it is after the second vaccination or the time is missing or not available, then study day is calculated as: date of assessment/event – date of the second vaccination + 1. If a subject did not receive the second vaccination, but received the third vaccination, study day after the second vaccination will be treated as missing, and only calculate in relative to the third vaccination.

- d) study day after the date of the third vaccination will be calculated as: date of assessment/event – date of the third vaccination + 1; if study day is on the same day as the third vaccination, date and time will be compared with the third vaccination date and time. If it is prior to the third vaccination, then study day is calculated as: date of assessment/event – date of the second vaccination + 1; If it is after the third vaccination or the time is missing or not available then study day is calculated as: date of assessment/event – date of the third vaccination + 1.

For GMT calculation, antibody values reported as below the lower limit of quantification (LLOQ) will be replaced by $0.5 \times \text{LLOQ}$. Values that are greater than the upper limit of quantification (ULOQ) will be converted to the ULOQ. Missing results will not be imputed.

The following **stages** are used for reporting and analysis purposes:

- Vaccination stage:

For assessments that will be collected throughout the study (eg, unsolicited AE), it consists first vaccination on Day 1 to the earliest date of (28 days after last vaccination [ie, the day of last vaccination and 27 subsequent days], discontinuation from the study, or death). If a subject receives three vaccinations, this stage starts at the first vaccination on Day 1 and continues through the earliest date of (28 days after 3rd vaccination, withdraw from study, or death).

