6.4.2. Analysis of Antibody-Mediated Immunogenicity Endpoints

For each group, the following evaluations will be performed at each time point at which blood samples are collected for antibody-mediated immunogenicity (unless otherwise specified):

- GMT of the serum anti-CMV neutralizing antibody titers against epithelial cell infection and anti-CMV neutralizing antibody titers against fibroblast infection will be provided at each time point with corresponding 95% CI. The 95% CIs will be calculated based on the t-distribution of the log-transformed values then back transformed to the original scale for presentation. GMT and corresponding 95% CI

will be plotted over time. The following descriptive statistics will be also provided at each time point: the number of subjects (n), median, minimum and maximum.

- GMRs of anti-CMV neutralizing antibody titers against epithelial cell infection and anti-CMV neutralizing antibody titers against fibroblast infection at each individual post-vaccination time point over pre-vaccination (eg, Visit Day 1 [baseline]) will be tabulated with 95% CI. The 95% CIs will be calculated based on the t distribution of the difference in the log-transformed values then back transformed to the original scale for presentation. GMR and corresponding 95% CI will be plotted over time.
- In the CMV-seronegative groups, proportion of subjects with titers above baseline GMT of all CMV-seropositive subjects at each timepoint after baseline (Day 1) will be tabulated.
- Proportion of subjects with a ≥ 2 -fold, 3-fold, and 4-fold increase in serum anti-CMV neutralizing antibody titers against epithelial cell infection and anti-CMV neutralizing antibody titers against fibroblast infection from Visit Day 1 (baseline) to post-vaccination time points will be tabulated with 2-sided 95% Clopper-Pearson CIs.
- Proportion of subjects with overall seroresponse in serum anti-CMV neutralizing antibody titers against epithelial cell infection and anti-CMV neutralizing antibody titers against fibroblast infection at each individual post vaccination time point will be tabulated with 2-sided 95% Clopper-Pearson CIs. Overall seroresponse is defined as subjects who either had an undetectable titer (LLOQ) at baseline and a $\geq 2 \times$ LLOQ titer after vaccination, or a detectable titer (\geq LLOQ) at baseline and at least a 4-fold increase of baseline titer after vaccination.

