- In the CMV-seropositive groups, proportion of subjects who achieve serum anti-CMV neutralizing antibody titers against epithelial cell infection and anti-CMV antibody titers against fibroblast infection greater than the third quartile of the serum anti-CMV antibody titers overall distribution at baseline (Day 1) will be tabulated.
- Anti-CMV neutralizing antibody titers against epithelial cell infection and anti-CMV neutralizing antibody titers against fibroblast infection will be displayed using reverse cumulative curves.
- For serum anti-CMV neutralizing antibody titers against epithelial cell infection and anti-CMV neutralizing antibody titers against fibroblast infection respectively, the GMT at Month 3, Month 7, Month 12, and Month 18 for each vaccination group, and

the ratio of GMT of mRNA-1647 **CCI**, mRNA-1647 **CCI**, and mRNA-1647 **CCI** vs. Placebo respectively, will be estimated based on an analysis of covariance (ANCOVA) model that will be carried out for CMV-seropositive groups and CMV-seronegative groups separately using the PP Set. For Month 3, the dependent variable will be the nAb at Month 3 with the vaccination group as a factor and the baseline values as covariate (if applicable, ie, for CMV-seropositive groups only). The GMT and corresponding 95% CI for each vaccination group, and the ratio of GMT of mRNA-1647 **CCI**, mRNA-1647 **CCI**, and mRNA-1647 **CCI** vs. Placebo respectively, together with corresponding 95% CI will be provided. A similar model at Month 7, Month 12, and Month 18 will be carried out for those who were CMV-seronegative groups, and CMV-seropositive groups separately using the PP set.

Similar analyses will be performed for gB-binding antibodies and Pentamer-binding antibodies as measured by ELISA.

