3. A Part 2 7-month interim analysis of safety and immunogenicity data collected from Visit Day 1 through Day 196 (Month 7) was performed after all Part 2 participants had completed 7 months of safety and immunogenicity assessments (data cutoff date 18 Feb 2022). Available safety and immunogenicity data from Visit Day 1 through the end of the trial for all Part 1 participants were also summarized as part of this interim analysis. Pre-identified Sponsor team members were unblinded to both treatment group-level results and individual listings. Study participants, Investigators, and study sites remained blinded until the completion of each individual participant's final study procedures, including final assessment and recording of MAAEs and SAEs, at which point the individual participant's treatment assignment may be unblinded using the IRT system to the Investigator, participant, Sponsor, and Sponsor representatives/delegates, as outlined in protocol Section 8.11 "Unblinding".
4. The final unblinded analysis of safety and immunogenicity data collected from Visit Day 1 through the end of the trial for all participants will be conducted when the database is cleaned and locked. Results of this analysis will be presented in a Clinical Study Report (CSR), including individual listings.

At an interim analysis when data from both Part 1 and Part 2 were available and in scope for the analysis, or at the final analysis when all participants in Part 1 and Part 2 have completed or discontinued from the study, data were/will be summarized and analyzed with Part 1 and Part 2 combined, unless otherwise specified.

7. Changes from Planned Analyses in Protocol

For the planned 7-month IAs, protocol Section 9.7 states "Available safety or immunogenicity data up to Day 336 (Month 12) may also be summarized as part of these interim analyses." However, at the time of planning the Part 2 7-month IA with the latest

data cutoff date of 18 Feb 2022 for Part 2 participants, all Part 1 participants either discontinued or completed the study up to the final visit at Month 18 for participants completing all 3 vaccinations. Therefore, the Part 2 7-month IA instead included all available safety and immunogenicity data from Visit Day 1 through the end of the trial for all Part 1 participants to make this analysis more comprehensive. This change did not impact the primary and/or key secondary objectives/hypotheses or the related statistical methods.

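### The seronegative ANCOVA in SAP 6.4.2 pools its residual variance with a placebo arm expected to have almost none, so the model-based GMT and ratio intervals are likely to be miscalibrated

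*SAP*

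**What the plan says.** SAP 6.4.2 (Analysis of Antibody-Mediated Immunogenicity Endpoints) states that the GMT of each vaccination group, and the ratio of each dose to placebo, "will be estimated based on an analysis of covariance (ANCOVA) model that will be carried out for CMV-seropositive groups and CMV-seronegative groups separately", on the PP Set, with 95% intervals for both. The baseline covariate applies to seropositive groups only, so in seronegatives the model is a one-way analysis of variance. No arm-specific variance is mentioned. The log scale is not stated for this model but is implied by the GMT.

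Three other rules bear on the placebo arm:

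- SAP 6.1: "antibody values reported as below the lower limit of quantification (LLOQ) will be replaced by" 0.5 × LLOQ.
- SAP 5.5, on membership of the PP Set: "Subjects who were CMV seronegative at Screening and became CMV seropositive at baseline (before or on 1st dose of study vaccination) will be excluded".
- SAP 6.2.2 defines positive baseline CMV serology as either neutralizing titer above LLOQ.

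SAP 6.4.2 also plans a descriptive GMT interval for each group at every time point: "The 95% CIs will be calculated based on the t-distribution of the log-transformed values then back transformed". The GMR over baseline gets the same treatment. Both use only that group's own data.

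SAP 6.5 says that at the final analysis "data were/will be summarized and analyzed with Part 1 and Part 2 combined".

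**The concern.** A common residual variance is reasonable when the arms have similar spread. Here one arm is expected to have nearly none. A seronegative placebo recipient in the PP Set should start below LLOQ and, unless infected, stay there, and each such result is recorded as the same number. A quarter of the participants would then pull the pooled variance down.

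This has three consequences. The model-based interval for each dose GMT is too short. A placebo GMT that does not vary is given an interval. That artificial placebo error then enters every dose/placebo ratio, most of all for the dose enlarged by Part 2, where the vaccine arm's own error is smallest. At stake are the width and coverage of the model-based intervals for the neutralizing antibody results. The GMT point estimates do not change.

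**Working it through.** **The plan's own figures.** The documents give no coverage or interval width. Their only quantitative design figures are the chances of seeing at least one AE at a 2% rate. These reproduce: 1 − 0.98^189 = 97.8% (stated > 95%) and 1 − 0.98^150 = 95.2% (stated > 90%).

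**Arm sizes (SAP 4.1).** Part 1, per dose: "Approximately 60 participants randomized 3:1 to receive either CCI of mRNA-1647 vaccine or placebo in a 0, 2, 6-month schedule". Three such cohorts give 45 vaccine per dose and 3 × 15 = 45 placebo. Part 2: "Approximately 80 participants randomized 3:1 to receive either CCI of mRNA-1647 vaccine or placebo", giving 60 vaccine at the selected dose and 20 placebo. Combined: vaccine 45, 45 and 105; placebo 65; N = 260; residual df = 260 − 4 = 256.

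**Assumptions for the base case.** Placebo SD is 0 and the three vaccine arms share one SD, s. The documents give neither.

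**Pooled variance.** Σ(nᵢ − 1)sᵢ² / (N − 4) = (44 + 44 + 104)s² / 256 = 192s²/256 = 0.75 s², so the pooled SD is 0.866 s.

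**Coverage of a dose-GMT interval.** 2Φ(t₂₅₆ × 0.866) − 1 = 2Φ(1.969 × 0.866) − 1 = 91.2%. Simulation (40,000 runs) gives 91.0%. The own-arm t interval gives 95.0–95.2% in the same runs.

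**Ratio to placebo.** SE inflation = 0.866 × √(1/n_d + 1/65) ÷ √(1/n_d).

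| Arm | SE inflation | Interval width vs own-variance interval | Coverage |
|---|---|---|---|
| n = 45 | 0.866 × 0.1939 / 0.1491 = 1.13 | 1.10 | 97.3% |
| n = 105 | 0.866 × 0.1578 / 0.0976 = 1.40 | 1.39 | 99.4% |

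**Placebo GMT.** Half-width on log10 = 1.969 × 0.866 s / √65. For an assumed s of 0.3 to 0.6 this is 0.063 to 0.127, an interval of ×/÷ 1.16 to 1.34 around a constant.

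**Sensitivity to sample size.** Part 1 sizes alone (45 in each of four arms): coverage 91.3%, ratio SE 1.22. The larger Part 2 option in Protocol 5.1 ("The Sponsor may enroll up to 502 participants"; arms 45/45/120, placebo 70): variance 207/276 = 0.75, coverage 91.2%, ratio SE up to 1.43. A 15% loss in every arm changes nothing material.

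**Sensitivity to placebo spread.** With placebo SD at 0.25, 0.5 or 0.75 of the vaccine SD, coverage is 91.5%, 92.4% or 93.7%, and the largest ratio SE inflation is 1.35, 1.23 or 1.10.

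**Sensitivity to placebo infections.** Assume a rise of 2 log10 per seroconverter. With k seroconverters among 65, the placebo variance is 4k(65 − k)/(65 × 64). For vaccine SD 0.3–0.6 log10:

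- One seroconverter: coverage 92–94%; ratio SE factor at n = 105 from 1.07 to 1.28.
- Three seroconverters: coverage 93–97%; the same factor from 0.88 to 1.13.

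**Sensitivity to unequal dose SDs.** With relative SDs of 1.3, 1 and 0.8 for the 45, 45 and 105 arms, coverage is 80%, 91% and 96%, and the ratio SE factors are 0.85, 1.11 and 1.72. In the reverse order (0.8, 1, 1.3), coverage is 98%, 95% and 86%.

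**The case against.** The strongest answer is that sound intervals are already planned. With no covariate, the model's GMT in seronegatives equals the plain GMT, and SAP 6.4.2 already reports that with an own-arm t interval. If baselines and placebo values all sit at 0.5 × LLOQ, the dose/placebo ratio equals the GMR over baseline, which is also reported with an own-arm interval. This stands. It limits the damage, but it does not make the model-based intervals correct, and the SAP does not say which set should be preferred.

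A reader might infer that the primary immunogenicity result or the dose choice is compromised. The documents do not support that. The primary endpoints (Protocol 3.2.1) are GMT, GMR over baseline and fold-rise proportions. Protocol 9.6.3 contains no ANCOVA, and the ratio to placebo is not a listed endpoint. There is no hypothesis testing, and the dose was chosen on the May 2020 interim subset (SAP 6.5).

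A reader might also take a constant placebo arm as a fact of the plan. The SAP does not say so. Screening serostatus is set by CMV IgG, infection after baseline is not a listed PP exclusion, and follow-up runs to Month 18. The inference is weaker at Months 12 and 18, and for ELISA if background exceeds LLOQ.

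Finally, a reader might extend the point to seropositives. The documents give no titer variances by arm, so nothing supports a claim there.

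**Conclusion.** Wrong as written; moderate severity. One shared residual variance does not suit seronegative arms in which placebo is expected to be nearly constant. Under the base-case assumptions, the model-based dose-GMT intervals cover about 91% instead of 95%. The ratio intervals are about 10% too wide for two doses and 39% too wide for the dose enlarged by Part 2.

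With no placebo infections and one SD common to the vaccine arms, these ratios do not depend on the size of that SD or on the LLOQ. Without those conditions the size changes, and the direction can too. It would therefore be too strong to say that the GMT intervals are always too narrow and the ratio intervals always too wide. What holds generally is that the accuracy of these intervals depends on how many placebo recipients acquire CMV and on how alike the dose SDs are, neither of which the plan controls. Reporting descriptive and model-based intervals together is not itself a fault.

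**What to change.** In SAP 6.4.2, for seronegatives only:

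- Estimate a separate variance for each arm. With no covariate, this amounts to using the own-arm t interval already planned in the same section as the GMT interval.
- Compute the dose/placebo ratio interval with a Welch-type standard error.
- When all placebo values are below LLOQ, label the ratio as relative to 0.5 × LLOQ.

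In SAP 6.4.4, state that the seronegative MMRM intervals share the common-variance limitation, or fit that model to the vaccine arms only. A group-specific unstructured covariance is not advised. It is degenerate for a constant placebo arm. With seven post-baseline visits it needs 28 parameters per group, and the smaller seropositive vaccine arms have about 24 × 3/4 = 18 participants.

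The cost is a few lines of SAP text and code and no new data, and SAP version 5.0 precedes the final database lock. The downside is wider model-based dose-GMT intervals in the base case: standard errors rise by 1/0.866 = 1.155, about 15%, and full widths by about 16% (n = 105) to 18% (n = 45) once the smaller degrees of freedom are counted. Ratio intervals shrink to about 0.72 (n = 105) and 0.91 (n = 45) of their pooled width.

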6.4.3. Analysis of CMI Endpoints

Descriptive summary statistics for the observed and change from baseline will be provided at each scheduled visit by serostatus group (ie, CMV-seropositive and CMV-seronegative groups) and vaccination group for CMI parameters, based on the PP Set for CMI. Descriptive statistics for the observed and change from baseline values will be plotted over time.

6.4.4. Sensitivity/Supportive Analysis

In the final analysis of antibody-mediated immunogenicity endpoints, the following sensitivity analyses may be performed to assess the impact of widened visit window and missing data due to COVID-19 pandemic.

1. In Part 1, protocol amendment 2 widened the visit window in response to the COVID-19 pandemic. A sensitivity analysis may be carried out to assess the impact on the widened visit windows on immunogenicity endpoints. In this sensitivity analysis, immunogenicity data which complied with the vaccination and/or immunogenicity assessment schedules under protocol amendment 2, but which did not comply with the schedules under protocol amendment 1, the last version of protocol before the protocol amendment 2, will be excluded from this sensitivity analysis.
2. A restricted maximum likelihood (REML)-based mixed-effect model for repeated measures (MMRM), a model-based missing data approach, will be used for the log-

transformed titer based on the PP set. MMRM is based on the assumption of missing at random.

The analysis will be carried out using SAS PROC MIXED and conducted for CMV-seropositive groups and CMV-seronegative groups separately. The model will include all available log-transformed anti-body titers at each post-baseline visit as the dependent variable, vaccination groups, visit (as a class variable), baseline values (if applicable, ie, for CMV-seropositive groups only), and interaction of vaccination group and visit as fixed effects, and subject as a random effect. An unstructured covariance structure will be used to model the within-subject errors. If the model fails to converge, a compound symmetry covariance structure will be considered. The degrees of freedom of the denominator will be approximated by the Kenward-Roger method. The geometric least squares mean (GLSM) and corresponding 2-sided 95% CI for the anti-body titers for each vaccination group will be provided by visit. In addition, the ratio of GLSM and the corresponding 2-sided 95% CI will be provided to assess the treatment difference between each of mRNA-1647 group **CCI** vs. the Placebo group at each visit. The GLSM, difference in GLSM, and corresponding 95% CI results in log-transformed scale estimated from the model will be back-transformed to obtain these estimates in the original scale.

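### In the CMV-seropositive groups, the optional MMRM changes the baseline adjustment as well as the handling of missing data, so a gap from the visit-wise ANCOVA cannot be attributed to missing data alone

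*SAP*

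**What the plan says.** SAP 6.4.4 introduces its analyses as optional ("the following sensitivity analyses may be performed") and gives their purpose: "to assess the impact of widened visit window and missing data due to COVID-19 pandemic". Item 2 is an MMRM on log-transformed titers in the PP Set, run separately by serostatus. Its fixed effects are vaccination group, visit, "baseline values (if applicable, ie, for CMV-seropositive groups only), and interaction of vaccination group and visit as fixed effects". On covariance it says: "An unstructured covariance structure will be used to model the within-subject errors". It adds a fallback: "If the model fails to converge, a compound symmetry covariance structure will be considered". The output is the ratio of each dose to placebo at each visit.

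SAP 6.4.2 estimates the same ratios by ANCOVA, also in the PP Set and by serostatus. The first model is specified thus: "the dependent variable will be the nAb at Month 3 with the vaccination group as a factor and the baseline values as covariate", with the covariate used in the seropositive groups only. Then: "A similar model at Month 7, Month 12, and Month 18 will be carried out".

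Protocol 8.8 schedules seven post-baseline antibody samples: Days 29, 56, 84, 168, 196, 336 and 504.

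**The concern.** A sensitivity analysis for missing data is easiest to read when it agrees with the analysis it checks if nothing is missing. Any difference can then be put down to the missing data. That property fails here in the seropositive groups. The ANCOVA lets baseline titer predict the later titer more strongly at one visit than at another. The MMRM fixes one coefficient across pre-dose samples (Days 56 and 168), samples 28 days after Doses 2 and 3 (Days 84 and 196) and late follow-up (Days 336 and 504). The SAP gives no reason to expect equal slopes at such different times.

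If the two sets of ratios disagree, the reader cannot tell whether missing data or the changed baseline adjustment is the cause. The two effects could also offset each other and give false reassurance.

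**Working it through.** **Inputs from the documents.** Seropositive planned numbers (SAP 4.1, 3:1 allocation): Part 1 has 3 x 24 = 72, that is 18 vaccinees per dose and 18 placebo. Part 2 has 120, that is 90 vaccinees and 30 placebo. With the parts combined (SAP 6.5), the groups are 18, 18, 18 + 90 = 108, and placebo 18 + 30 = 48, in total 192.

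**Assumptions.** The documents give no baseline slopes, SDs or correlations. Assumed on the log10 scale: baseline SD 0.3-0.5, residual SD 0.3, within-subject correlation 0.6, and the same baseline distribution in every group.

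**Step 1: where the gap comes from.** With complete data, let dY be the dose-minus-placebo difference in mean log10 titer at visit j, and dX the same difference at baseline.

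- ANCOVA: dY - b_j x dX, with b_j specific to the visit.
- MMRM as written: dY - b x dX, with one b for all visits.
- ANCOVA minus MMRM: (b - b_j) x dX.

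**Step 2: check on one simulated complete data set** (18/18/108/48, the four ANCOVA visits, REML, unstructured covariance). The common slope is 0.43225.

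| | Month 3 | Month 7 | Month 12 | Month 18 |
|---|---|---|---|---|
| Visit slope b_j | 0.38246 | 0.35181 | 0.44385 | 0.56887 |
| ANCOVA contrast | -0.05790 | -0.07897 | -0.05626 | -0.03451 |
| MMRM as written | -0.05982 | -0.08206 | -0.05581 | -0.02924 |
| MMRM with baseline-by-visit | -0.05790 | -0.07897 | -0.05626 | -0.03451 |
| ANCOVA SE | 0.04959 | 0.05175 | 0.05207 | 0.05245 |
| SE, MMRM as written | 0.04967 | 0.05198 | 0.05202 | 0.05319 |
| SE, MMRM with baseline-by-visit | 0.04959 | 0.05175 | 0.05207 | 0.05245 |

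The formula fits. At Month 18 the gap is -0.03451 + 0.02924 = -0.00527, and b - b_j = -0.13662, so dX = 0.0386. Month 3 gives 0.00192 / 0.04979 = 0.0386. With the interaction, estimates and standard errors match the ANCOVA to five decimals. With no baseline term in either model, as planned for seronegatives, the MMRM and ANCOVA also match to five decimals.

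**Step 3: approximate size for an 18-person dose against 48 placebo.** The SD of dX is SDx x sqrt(1/18 + 1/48) = SDx x 0.2764. The RMS gap is about |b_j - b| x SD(dX). The SE ratio (MMRM to ANCOVA) is about sqrt(1 + (b_j - b)^2 x SDx^2 / 0.3^2).

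| Slope departure | Baseline SD 0.3: gap, SE ratio | Baseline SD 0.5: gap, SE ratio |
|---|---|---|
| 0 | about 0, 1.00 | about 0, 1.00 |
| 0.1 | 0.0083 log10 = 1.9%, 1.005 | 0.0138 = 3.2%, 1.014 |
| 0.2 | 0.0166 = 3.9%, 1.020 | 0.0276 = 6.6%, 1.054 |
| 0.3 | 0.0249 = 5.9%, 1.044 | 0.0415 = 10.0%, 1.118 |

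**Step 4: simulation of complete data at Month 7, same contrast.**

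- Equal slopes: RMS gap 0.9%, no loss of precision.
- Baseline SD 0.5, slopes 0.35-0.65: gap 6%, at least 12% in 1 trial in 20, SD of the estimate 5% larger.
- Baseline SD 0.5, slopes 0.25-0.75: gap 9%, at least 19-20% in 1 trial in 20, SD 6-9% larger.
- Across all slope patterns tried with marked variation: gap 5-11% and SE 1.5-10% larger at baseline SD 0.5; gap 3-6% and SE 0.3-3% larger at baseline SD 0.3.
- The mean gap was at most 0.002 log10.

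**Step 5: the 108-person dose.** Chance imbalance is smaller, so the gap is too. The SD ratio was 0.997-1.002 with equal slopes, at most 1.011 with slopes 0.60-0.75, and at most 1.083 with slopes 0.35-0.65.

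**The case against.** The strongest reply is that a common baseline slope is a legitimate, prespecified, simpler model. It is as precise as the ANCOVA when slopes are similar, and nothing in the documents shows that they are not. That stands: the size of the effect is conditional.

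The stakes are also low. The MMRM is optional, the study tests no hypothesis (SAP 4.2), and the primary immunogenicity endpoints are GMT, within-subject GMR and fold-rise proportions, which use neither model. SAP 6.5 records that the Part 2 dose was chosen from the Month 3 interim analysis, so dose selection does not depend on this comparison.

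The gap is small beside the uncertainty. For 18 against 48, the ANCOVA SE is about 0.3 x 0.2764 = 0.083 log10, so the 95% interval spans about 1.5-fold each way. The RMS gap is roughly 0.1-0.5 SE.

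A reader might infer three stronger things, none of which the documents support:

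- That all participants are affected. In the seronegative groups (180 + 80 = 260 of 452 planned) neither model contains baseline, and the two coincide with complete data under unstructured covariance.
- That the MMRM loses precision as a rule. It does so only at visits whose slope departs from the common one.
- That the MMRM is biased. The gap is chance imbalance at baseline multiplied by a slope difference, and it averages about zero.

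What survives is the point about attribution. The SAP does not name the comparator, but the ANCOVA is the planned analysis that yields the same between-group ratios. The two differ in more than the handling of missing data.

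**Conclusion.** The point holds for the seropositive groups, as a matter of interpretability. That the two models differ with complete data follows from the SAP text and needs no assumption beyond unequal fitted slopes. The size does rest on assumptions: close to zero with equal slopes, and roughly 3-11% RMS in the Month 7 ratio for an 18-person dose if slopes vary moderately to strongly, with an MMRM standard error about 0-10% larger where the slope departs from the common one. The range comes from baseline SD 0.3-0.5 log10, residual SD 0.3 and correlation 0.6; the documents neither confirm nor exclude these values. Error rates and the primary endpoint analyses are not affected.

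**What to change.** In SAP 6.4.4 item 2, add the interaction of baseline log10 titer with visit to the seropositive MMRM. The fixed effects become group, visit, group-by-visit, baseline and baseline-by-visit. The seronegative model stays as it is.

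With complete data the point estimates then equal the visit-wise ANCOVA, and the standard errors also match under the unstructured covariance. If the compound symmetry fallback is used, standard errors can still differ without any missing data. The SAP should say so and require it to be noted whenever the two analyses are compared.

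The cost is one model term: 7 - 1 = 6 parameters on about 192 participants. When slopes are in fact equal, the simulations showed no measurable loss of precision from including it. SAP section 1 places version 5.0 before the final database lock, and this MMRM belongs to the final analysis.
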